### **2.3.2. Benefit Assessment**

PF-07321332 (nirmatrelvir) has been shown to have SARS-CoV-2 antiviral activity in vitro and in Study C4671005 and is intended to reduce viral titers, thereby reducing the duration and severity of symptoms and the risk of hospitalization and mortality in SARS-CoV-2 infected patients. Participants in Study C4671005 who received PF-07321332 (nirmatrelvir)/ritonavir within 5 days of symptom onset had an 88% (95% CI: 75%, 94%) reduction in risk of COVID-19-related hospitalization or death. On this basis, the potential benefit to individual study participants who receive the study intervention may include a shorter time to clinical recovery, prevention of hospitalization, and a lower probability of progressing to more severe illness or death. The potential benefit of the study is that it may provide a new treatment option for non-hospitalized severe renal impairment patients with COVID-19 who are at risk of progression to severe disease. In the context of the global pandemic public health emergency, this treatment could play an important role in alleviating current pressures on health care systems globally.

### **2.3.3. Overall Benefit/Risk Conclusion**

Considering the current COVID-19 global pandemic and the high burden of both mortality and morbidity and the potential for future epidemic outbreaks, the lack of readily available outpatient treatment options, and the measures taken to minimize risk to participants in this study, the potential risks identified in association with PF-07321332 (nirmatrelvir)/ritonavir are justified by the anticipated benefits that may be afforded to severe renal impairment participants with COVID-19.

### 3. OBJECTIVES, ENDPOINTS, AND ESTIMANDS

Objectives	Endpoints	Estimands
Primary: 

To describe the safety and tolerability of PF-07321332 (nirmatrelvir)/ritonavir in adult participants with COVID-19 and severe renal impairment.

	Primary: 

Incidence of TEAEs.

Incidence of SAEs and AEs leading to discontinuations.

	Primary: 

Not Applicable.

Secondary: 

To evaluate the effect of severe renal impairment on the PK of PF-07321332 (nirmatrelvir) in participants not on HD.

To evaluate the effect of severe renal impairment on the PK of PF-07321332 (nirmatrelvir) in participants on HD.

To evaluate the effect of HD on the PK of PF-07321332 (nirmatrelvir).

	Secondary: 

Plasma PF-07321332 (nirmatrelvir) PK parameters including <math>C_{max}</math>, <math>CL/F</math>, <math>Vz/F</math>, <math>AUC_{0-\tau}</math>, <math>t_{1/2}</math>, and <math>C_{trough}</math> estimated from the population PK model.

HD clearance (CLd) of PF-07321332 (nirmatrelvir).

Fraction of PF-07321332 (nirmatrelvir) dose removed from the body by dialysis (Fd).

	Secondary: 

Not Applicable.

Not Applicable.

CCI		

### 4. STUDY DESIGN

#### 4.1. Overall Design

This is a Phase 1, open-label, multi-center, single arm study in approximately 24 non-hospitalized adult participants with COVID-19 and severe renal impairment and not yet receiving intermittent HD (Cohort 1) and severe renal impairment receiving intermittent HD (Cohort 2). The following Cohorts will be enrolled:

- Cohort 1: Severe renal impairment (defined as eGFR <30 mL/min/1.73 m^2) not on HD and mild-to-moderate COVID-19 disease with confirmed SARS-CoV-2 infection and initial onset of signs/symptoms attributable to COVID-19 within 5 days prior to the day of treatment assignment.

- Cohort 2: Severe renal impairment on HD and mild-to-moderate COVID-19 disease with confirmed SARS-CoV-2 infection and initial onset of signs/symptoms attributable to COVID-19 within 5 days prior to the day of treatment assignment.

All eligible participants will be assigned to receive a single dose of PF-07321332 (nirmatrelvir)/ritonavir 300 mg/100 mg orally on Day 1 followed by PF-07321332 (nirmatrelvir)/ritonavir 150 mg/100 mg QD from Day 2 to Day 5. Single dose PK study (Study C4671011) of PF-07321332 (nirmatrelvir)/ritonavir in mild, moderate, and severe renal impairment showed that the PF-07321332 (nirmatrelvir) exposure is approximately 3-fold higher and CL/F is 67% lower in severe renal impairment participants relative to healthy volunteers. Published literature as well as internal data showed there is minimal to no effect of renal impairment on ritonavir PK. Ritonavir 100 mg QD or BID dose has been used for several protease inhibitors (eg, darunavir) with small difference in dose normalized Ctrough of protease inhibitors. Additionally, the PK of PF-07321332 (nirmatrelvir) with 100 mg QD of ritonavir in severe renal impairment participants is expected to be similar to those of healthy participants taking 100 mg BID of ritonavir. Therefore, the ritonavir dose of 100 mg QD was selected for this study. The total study duration is up to 38 days and includes a 1-to 2-day screening period where participants can be screened on one day and randomized the next day or screened and randomized on the same day. Screening procedures can be performed over two days, but the participant must be randomized by the second day (Day 1) and begin study treatment. Therefore, Screening and Randomization can take no longer than 2 consecutive days. After Screening, the participants takes study intervention for 5 days and completes the safety follow-up period through Day 34. Continued collection of ongoing safety information through SAE resolution will occur as applicable.

For PK assessments in severe renal impairment participants not on HD, sparse PK samples will be collected on Day 1 through 5 of dosing. This should be collected using a Tasso device and a venous blood sample as specified in the [SoA](#).

For PK assessments in severe renal impairment participants on HD, samples will be collected on Days 1 through 5 of dosing with respect to the participant's dialysis sessions during treatment. If at home, this should be collected using a Tasso device or may be done at an in-person visit, unless otherwise specified in the [SoA](#). During HD, venous port (entering dialyzer) and arterial port (exiting the dialyzer) blood samples will be collected at 0, 0.5, 1, 2, 3 and 4 hours post the start of dialysis.

This study will use the program-level E-DMC. The E-DMC is independent of the study team and includes only external members. The E-DMC charter describes the role of the E-DMC in more detail for this study.

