**PK SAMPLING SCHEMA 2 – COHORT 2: HD cohort with 1st Dose on HD day that is Monday**

Study Day	Day 1 – HD MONDAY	Day 2 – no HD TUESDAY	Day 3 – HD WEDNESDAY	Day 4 – no HD THURSDAY				Day 5 – HD FRIDAY
PF-07321332 (nirmatrelvir)/ritonavir administration	X b	X	X b		X			X b
Hours after dosea	1 – 3		Before and During HD	0	0.5 – 3	4 – 8	9 – 15	Before HD start
PK blood sampling (Tasso)	X f		X c	X c	X f	X f	X f	[X c ]
PK blood sampling during HD (arterial and venous ports)			X d					X e
Hematology blood sample (hematocrit)			X i					
Blood:Plasma Ratio sample (venous)	X h		X g, h		X h			[X g, h ]

- a. Hours are in reference to the QD dose of PF-07321332 (nirmatrelvir)/ritonavir on each study day. The Day 1 dose should be taken at the clinic visit.
- b. On dialysis days, participants will take study intervention as soon as feasible after HD.
- c. Tasso blood sample: Tasso device placed by participant, caregiver, home health provider, or other healthcare provider (as appropriate).
- d. Venous blood samples: HD staff to obtain PK blood samples from the HD filter arterial port and the venous port at 0 hr (prior to start of HD) and at 0.5, 1, 2, 3, and 4 hours post start of dialysis.
- e. Day 5 PK blood sample: If participant goes to HD treatment prior to going to investigational site on Day 5, then HD staff to obtain this venous sample prior to the start of dialysis from the venous HD line. If participant goes to investigational site prior to going to HD on Day 5, then investigational site staff can obtain PK sample using the Tasso device.
- f. Tasso blood samples: After dosing study drug, Tasso device placed by participant, caregiver, home health provider, or other healthcare provider (as appropriate). Collect the consecutive PK samples within the prescribed windows with each sample taken a minimum of 2 hours apart.
- g. Blood:Plasma Ratio venous sample: Collect at 0 hr prior to start of HD.

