**PK SAMPLING SCHEMA 11 - COHORT 2: HD cohort with 1st Dose on non-HD day Thursday**

Study Day	Day 1 - no HD THURSDAY	Day 2 – HD FRIDAY	Day 3 – no HD SATURDAY				Day 4 - no HD SUNDAY	Day 5 – HD MONDAY
PF-07321332 (nirmatrelvir)/ritonavir administration	X	X b		X			X	X b
Hours after dose a	1 - 3	At end of HD (prior to dosing)	0	0.5 - 3	4 - 8	9 - 15	0	Before and During HD
PK blood sampling (Tasso)	X c	[X d ]	X d	X e	X e	X e	X d	X d
PK blood sampling during HD (arterial and venous ports)								X c
Hematology blood sample (hematocrit)								X i
Blood:Plasma Ratio sample (venous)	X h	[X h ]		[X h ]			[X h ]	X g, h

- a. Hours are in reference to the dose of PF-07321332 (nirmatrelvir)/ritonavir on each study day. The Day 1 dose should be taken at the clinic visit.
- b. On dialysis days, participants will take study intervention as soon as feasible after HD.
- c. Venous blood samples: HD staff to obtain PK blood samples from the HD filter arterial port and the venous port at 0 hr (prior to start of HD) and at 0, 0.5, 1, 2, 3, and 4 hours post start of dialysis.
- d. Tasso blood sample: Tasso device placed by participant, caregiver, home health provider, or other healthcare provider (as appropriate).
- e. Tasso blood samples: After dosing, Tasso device placed by participant, caregiver, home health provider, or other healthcare provider (as appropriate). Collect the consecutive PK samples within the prescribed windows with each sample taken a minimum of 2 hours apart.
- f. Venous blood sample: at end of HD prior to dosing, one sample will be drawn from the venous port.
- g. Blood:Plasma Ratio venous sample: Collected at 0 hr prior to start of HD.
- h. Blood:Plasma Ratio venous sample: Collected immediately before or after a Tasso sample but no longer than 15 minutes between the samples. The blood:plasma ratio sample tube is divided into 1 blood sample (in a cryovial) and, after centrifugation, 1 plasma sample (in another cryovial) (reference the Central Lab Manual). Collect blood:plasma ratio samples on Day 1 and Day 5. If one sample is missed, it may be collected on Day 2, Day 3 or Day 4. Always collect a corresponding Tasso sample for each blood:plasma ratio sample.

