### 8.5.2. Hemodialysis

Participants assigned to Cohort 2 will begin study intervention either on a HD treatment day or non-HD treatment day. The day of the participant's first IP dose, either on an HD day or on a non-HD day (ie, Treatment Day 1) will determine the subsequent PK sample schedule as described in the [PK Sampling Schema](#).

Participants beginning IP administration on an HD treatment day (ie, Treatment Day 1) will have PK samples collected per the [PK Sampling schema](#) in Section 1.3 including samples drawn from HD lines before and during HD treatment days. Obtain blood samples for **hematology (hematocrit)** at time 0 (venous port sample) and time of the last PK draw (venous port sample) on dialysis, to be used for dialysis clearance (CLd) calculations. Time 0 is defined as the time period prior to the start of the HD blood pump.

If the participant is assigned to begin IP treatment (ie, Treatment Day 1) on a non-HD day, the participant will have samples collected per the [PK Sampling Schema](#) in Section 1.3. Obtain blood samples for hematology (hematocrit) at time 0 (venous port sample) and time of the last PK draw (venous port sample) on dialysis, to be used for dialysis clearance (CLd) calculations. Time 0 is defined as the time period prior to the start of the HD blood pump.

Additional details regarding the HD treatment will be captured in the database (refer to CRF completion guidelines).

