6.2.2. HD clearance (CL_d) of PF-07321332 (nirmatrelvir)

Hemodialysis clearance (CL_d) of nirmatrelvir will be calculated using the following relationship:

$$CL_d = [(C_{in} - C_{out}) / C_{in}] \times [Q_b \times (1 - HCT)]$$

where C_{in} and C_{out} are plasma concentrations measured in blood samples entering and exiting the dialyzer, respectively; Q_b and HCT are blood flow rate entering the dialyzer and hematocrit measured at each collection time, respectively. Individual time point CL_d values obtained using this method will be used to calculate an average subject CL_d.

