6.2.3. Fraction of PF-07321332 (nirmatrelvir) dose removed from the body by dialysis (F_d)

Fraction of nirmatrelvir dose removed from the body by dialysis (F_d) will be calculated as follow:

[figure not shown]
$$F_d = 100\% \times A_d / Dose$$

where A_d is the amount of drug removed by the dialysis and is calculated as follows:

[figure not shown]
$$A_d = CL_d \times AUC_{t_0-t_1}$$

where for $AUC_{t_0-t_1}$, t_0 marks the start time and t_1 the termination of the hemodialysis session.

CCI

CCI

CCI

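### Protocol 4.1 names the dialyzer ports in reverse of ordinary usage and is the only text linking port labels to Cin and Cout; if site and analyst follow different conventions, CLd and Fd take the wrong sign

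*Protocol*

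**What the plan says.** **Port names and direction.** Protocol 4.1 (Overall Design) states: "venous port (entering dialyzer) and arterial port (exiting the dialyzer) blood samples will be collected". Six draws are scheduled over a session, the first at 0 h and the last at 4 h.

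**What staff are told to do.** The Cohort 2 schemas (Protocol 1.3, PK Sampling Schemas 2 to 12) instruct by port name only. Schema 2, footnote d, reads: "HD staff to obtain PK blood samples from the HD filter arterial port and the venous port at 0 hr", followed by the later times. No schema says which port lies upstream of the dialyzer.

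**What the analyst is told to do.** SAP 6.2.2 gives CLd = [(Cin - Cout)/Cin] x [Qb x (1 - HCT)], with Cin and Cout defined as "plasma concentrations measured in blood samples entering and exiting the dialyzer, respectively". No port is named. It adds: "Individual time point CL_d values obtained using this method will be used to calculate an average subject CL_d". SAP 6.2.3 sets Ad = CLd x AUC(t0-t1) and Fd = 100% x Ad/Dose, where "t_0 marks the start time and t_1 the termination of the hemodialysis session". It does not say which concentration series supplies the AUC.

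**Hematocrit.** Protocol 8.5.2 and the schema footnotes take the hematocrit for CLd from the venous port, at time 0 and at the last PK draw. SAP 6.2.2 applies HCT to the blood flow entering the dialyzer.

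The synopsis lists CLd and Fd as the two endpoints for the objective on the effect of HD on nirmatrelvir PK.

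**The concern.** In general hemodialysis usage the arterial line carries blood to the dialyzer and the venous line returns it. The documents do not define these terms elsewhere, so this is outside usage and not a rule of the protocol. Protocol 4.1 has it the other way round.

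The dialysis unit works from the schemas, which give port names. The analyst works from the SAP, which gives positions. Within the two documents the only bridge is one parenthetical in 4.1, and it does not match how dialysis staff would ordinarily name the ports. A unit that labels by ordinary usage and an analyst who maps through 4.1 would exchange Cin and Cout. The mirror case does the same: a unit that labels by 4.1 and an analyst who maps by ordinary usage.

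At stake are the sign and size of CLd, and through it Ad and Fd. The study is described as an "open-label, multi-center, single arm study in approximately 24 non-hospitalized adult participants", so different centers could label differently.

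**Working it through.** The documents state no value for CLd or Fd, so there is no plan figure to reproduce. The check follows from the SAP formulas.

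**1. Is 4.1 the only bridge?** Three other texts bear on port position, and none settles it.
- Schema 11, footnote f: "Venous blood sample: at end of HD prior to dosing, one sample will be drawn from the venous port". It does not say whether the pump is running, and no cell of the extracted Schema 11 table carries that footnote mark.
- Schemas 2 and 3, footnote e, name the venous HD line, but before dialysis starts.
- The venous-port hematocrit paired with entering flow fits the naming in 4.1 but does not establish it.

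**2. Effect of a swap on one pair.** Inputs: E is the true extraction ratio, so the exiting concentration is (1 - E) times the entering one. Write Qp = Qb x (1 - HCT).
- Correct: CLd = +E x Qp.
- Swapped: [(1 - E) - 1]/(1 - E) x Qp = -E/(1 - E) x Qp.
- Ratio, swapped to correct: -1/(1 - E), free of Qb and HCT.

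E, Qb and HCT are not in the documents. I assume E of 0.2, 0.3 and 0.4, Qb 300 mL/min and HCT 0.35, so Qp = 300 x 0.65 = 195 mL/min.

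| E | Correct CLd (mL/min) | Swapped CLd (mL/min) | Ratio |
|---|---|---|---|
| 0.2 | 39.0 | -48.8 | -1.25 |
| 0.3 | 58.5 | -83.6 | -1.43 |
| 0.4 | 78.0 | -130.0 | -1.67 |

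The 0 h pair cannot reveal a swap. Protocol 8.5.2 says "Time 0 is defined as the time period prior to the start of the HD blood pump", so both ports should then give nearly the same value. If that pair is averaged in as zero, both columns shrink by 5/6 and the ratio is unchanged.

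**3. Effect on Fd.** Fd is proportional to CLd x AUC.
- If the AUC uses the true entering series, the Fd ratio equals the CLd ratio.
- If the AUC uses the same swapped series, the AUC is smaller by about (1 - E) and most of the size error cancels. With the common 0 h point and the trapezoid over the scheduled times, the ratio is -[1 + 0.25 h x E/(1 - E) x C(0)/AUC]. I took mono-exponential decline with CL/F 2.27 L/h and Vz/F 43.8 L, from Protocol Table 1 (100 mg / 44040 ng*hr/mL; 2.27 x 13.37/0.693), Qb 250 to 400 mL/min and HCT 0.30 to 0.35. The ratio is then -1.02 to -1.06: the sign is wrong and the size nearly right.

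**4. Mixed labelling.** With k of 12 Cohort 2 participants swapped and a common E, the cohort mean as a share of the true mean is (12 - k)/12 - (k/12)/(1 - E).

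| k | E 0.2 | E 0.3 | E 0.4 |
|---|---|---|---|
| 1 | 0.81 | 0.80 | 0.78 |
| 2 | 0.63 | 0.60 | 0.56 |
| 3 | 0.44 | 0.39 | 0.33 |
| 4 | 0.25 | 0.19 | 0.11 |

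At E 0.3 and k = 3: 0.75 - 0.25/0.7 = 0.393, and 0.393 x 58.5 = 23.0 mL/min, counting the during-dialysis pairs only. The mean crosses zero at k = 12(1 - E)/(2 - E), which is 5.3, 4.9 and 4.5 at the three values of E. Up to four swapped participants therefore leave a positive but attenuated mean.

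**The case against.** **No internal contradiction.** A reader might infer that the documents contradict themselves on the ports. They do not. Nothing in either document conflicts with 4.1, and the venous-port hematocrit is compatible with it. That the naming is reversed rests on general dialysis usage. This stands: from the documents alone it is an ambiguity with a bad consequence, not an inconsistency.

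**The SAP formula is sound.** Cin and Cout are defined by physical position, and an analyst who applies them by true flow direction makes no error. This also stands. But the samples arrive with port labels, and the SAP does not say how to turn a label into a position.

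**A swap would be seen.** Clearance is calculated per participant, and a value near -84 mL/min is impossible. A full swap would be noticed and could be undone, because both samples exist. That is right for a full swap. In the mixed case the individual values are still negative, so anyone who inspects them will find the problem; the attenuated mean survives only if nobody does. Neither document asks for such a check. The provision in SAP 5.3 for anomalous concentrations concerns the concentration summaries, and a swapped pair consists of two plausible concentrations.

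**The mapping may be settled elsewhere.** The laboratory manual, the CRF completion guidelines and the Analysis and Reporting Plan cited in SAP Appendix 2.2 are not in the file. Any of them may fix the port positions. If one fixes them by ordinary naming, 4.1 would still have to be brought into line.

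**Conclusion.** The concern holds in a conditional form. Protocol 4.1 is the sole link in the protocol and SAP between port names and Cin/Cout, and its naming runs against ordinary usage. A mismatch of conventions between site and analyst, in either direction, multiplies during-dialysis CLd by -1/(1 - E) and makes Fd negative. A shared convention, whichever it is, gives the correct CLd.

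A reader might infer that the planned CLd and Fd will come out negative or biased. The documents do not support that: they do not show how sites label or how the analyst will map. The CLd ratios depend only on the assumed E; the mL/min figures also need the assumed Qb and HCT.

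The realistic risk is mixed labelling that goes unchecked, for example a Cohort 2 mean at 39% of its true value with 3 of 12 swapped at E 0.3. Severity is modest: it should be fixed, but it touches only the secondary hemodialysis endpoints, and the primary safety endpoints are unaffected.

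**What to change.** 1. Ask the sites, and check the laboratory manual, which physical position each port label denotes.
2. In SAP 6.2.2, define Cin as the pre-dialyzer sample and Cout as the post-dialyzer sample, with the confirmed port name for each. Make Protocol 4.1 match the confirmed mapping; if ordinary naming is confirmed, that is arterial entering and venous exiting.
3. Add a per-session check that Cin exceeds Cout for the 0.5 to 4 h pairs. A reversed session should raise a label query before CLd is averaged, not an automatic exchange of values.
4. State in SAP 6.2.3 that AUC(t0-t1) uses the entering series, which a CLd normalized to Cin already implies.
5. Under the confirmed mapping, state whether the venous-port hematocrit is a pre- or post-dialyzer value, and reconcile it with the entering flow Qb. If the venous port proves to be downstream, the last-draw hematocrit is an exiting value; the pre-pump one is not affected. The documents do not allow the size of that effect to be estimated.

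The cost is one labelling query, a sign check on existing pairs, a few sentences in the SAP, and one parenthetical in 4.1. A change to 4.1 is a protocol amendment with the approvals that brings (Protocol 10.1.1), so it can wait for the next one; the SAP text and the check need not. No sample is added, moved or retimed.

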#### 4.2. Scientific Rationale for Study Design

SARS-CoV-2 is the causative agent of COVID-19. SARS-CoV-2 is an enveloped, positive sense single-stranded RNA virus with a glycoprotein spike on the surface. Cell entry requires binding of the spike protein to the cellular receptor ACE-2 and priming of the spike glycoprotein by the host cell serine protease TMPRSS2.

Given the limited data available in severe renal impairment for COVID-19 treatment options and request by FDA during consideration of the EUA for PF-07321332 (nirmatrelvir)/ritonavir to study PF-07321332 (nirmatrelvir) in this population, the study design is in accordance with available draft FDA guidance and takes into consideration the clinical course of these patients when affected by COVID-19 both on and not on HD.

The study population will be divided into a non-HD cohort and a HD cohort with severe renal impairment with awareness that they may be on several medications to be used with caution when taken in conjunction with PF-07321332 (nirmatrelvir)/ritonavir. Therefore, the prohibited medications will be limited to those that are contraindicated per the EUA label, while deferring to clinical judgement by the investigator as well as consultation with the Sponsor for other listed medications to be used with caution.

The proposed PK sampling schedule for participants not on HD will provide flexibility around the participant's schedule considering the study will be conducted in an outpatient setting and maintains the ability to provide close monitoring for safety. In the HD cohort, the PK schedule takes into consideration the schedule of intermittent HD given three times per week while also maintaining an appropriate dosing schedule to maintain an effective exposure while treating their COVID-19 infection and will inform the effect of HD on the PK of PF-07321332 (nirmatrelvir).

